TITLE OF THE STUDY: A comparative efficacy study: bioengineered living dermal replacement tissue vs. non-viable extracellular matrix for the treatment of non-healing diabetic foot ulcers.

ClinicalTrials.gov ID: NCT01450943
Date: February 27, 2019

PROTOCOL SUMMARY

TITLE OF THE STUDY: A comparative efficacy study: bioengineered living dermal replacement tissue vs. non-viable extracellular matrix for the treatment of non-healing diabetic foot ulcers.

PHASE: Equivalence Study

METHODOLOGY: Randomized, controlled, stratified, prospective

STUDY DURATION: 8 weeks

FOLLOW-UP: 16 weeks

STUDY CENTERS: 2 centralized study locations (Mather and Martinez Wound Clinics)

Note: Satellite clinics (Redding, Chico, Oakland and Fairfield) will refer patients to the study locations

NUMBER OF SUBJECTS: 3 treatment arms, 57 subjects per arm for a total of 171

STUDY OBJECTIVES: The primary objective of this study is to assess the effectiveness of cellular dermal replacement tissue vs. non-viable extracellular matrix (ECM) for the treatment of non-healing diabetic foot ulcers. The primary endpoint will be the measurement of wound closure at 12 weeks, secondary outcomes will be measured at 20 weeks and the rate of healing in each treatment arm.

Secondary objective of study is to determine cost effectiveness of the bioengineered cellular vs. acellular ECM products. Cellular ECMs (Dermagraft®) are costly devices, \$1800 per application, difficult to use and time sensitive (weeks). The acellular ECM, (Oasis®) is easier to use and at a cost \$80 per application and has a longer shelflife (2 years). These devices typically require multiple applications, on a weekly basis. If the findings show that these devices are equivalent, then the use of acellular ECM would lead to significant savings for the VA. Genetic markers of non-healing vs. healing diabetic ulcers will also be investigated, which will be useful information in predicting healing potential.

INCLUSION CRITERIA:

Subjects must meet all of the following inclusion criteria to enroll in the study:

1. Patients with ICD-9 codes of diabetic foot ulcer or other foot ulcer present for at least 4 weeks (any location on the foot, no more than 1 ulcer on the target limb).
2. Diagnosis of diabetes with either Type 1 or 2, and HbA1c less than 10%.
3. Over the age of 18 and younger than 85 years of age.
4. Based on the Curative Health Services Classification, subjects with a Grade 2 foot ulcer, full thickness and subcutaneous tissue that extend through the dermis but without tendon, muscle, capsule or bone exposure.
5. Area greater than or equal to 1.0 cm² and less than or equal to 25.0 cm² post debridement.
6. Foot ulceration with no clinical signs or symptoms of infection, as determined with clinical assessment of 2 or more signs of inflammation, and quantitative analysis of bacterial load of the wound. No systemic signs of infection, such as fever/chills, nausea or vomiting, and normal CBC.

- a) A sample of the wound after debridement with curettage technique will be taken for quantitative analysis of bacterial load. If findings of 1 x 105 CFU per gram of tissue, the wound will be considered subclinical infected and excluded from study.
- b) Lab test taken at start of study, CBC—white blood count within normal range.
7. Patients will be required to have an assessment for arterial insufficiency, which includes a formal ankle-arm index. If the ankle-arm index is equal to or greater than 0.8 and less than 1.4 or a toe-arm index is equal to or greater than 0.6 will be eligible. Note: Patients that have inconclusive physical examination or indirect physiologic testing (ankle-arm index) will require an arterial duplex studies that can image directly the arterial flow velocities and perfusion to the distal extremity or computed tomography angiography and conventional angiography, which may be considered as a subset group if findings show no arterial insufficiency per vascular surgeon consultant. In addition, patients that undergo revascularization procedure and do meet ABI requirement post-intervention will be included in the study as a subset group.
8. Females of childbearing age potential, with negative serum pregnancy test and not lactating during length of the study.
9. Willingness to comply to wound care assigned and attend follow-up visits.

EXCLUSION CRITERIA:

Those subjects will be excluded from the study with any of the following reasons:

1. Diagnosis of cancer, treatment with immunosuppressive or chemotherapeutic agents, radiotherapy or systemic corticosteroids less than 30 days before enrollment.
2. Immunocompromised diseases (HIV/AIDS).
3. Bleeding disorders.
4. Connective tissue diseases.
5. Pregnant women.
6. History of drug or alcohol abuse within one year of the study.
7. Infected wounds or osteomyelitis (confirmed by bone biopsy, MRI or bone scan).
8. Active Charcot as described by Saunder's classification system.
9. Poor nutritional status, Albumin level < 2.9.
10. Ulceration size less than 1.0 cm² or greater than 20 cm².
11. Porcine allergy.
12. Chemistry tests serum creatinine, 2 times above the upper limits and LFTs 3 times above the upper limits.

TREATMENT: Total duration of study per subject: Up to 22 weeks (Includes to 2 weeks of screening and up to 12 weeks until the end of the follow-up period).

DURATION OF ADMININSTRATION: 8 weekly applications (starting at Visit 4/Week 1).

STUDY DESIGN: This is a randomized, single-blinded, four-armed controlled clinical equivalence trial comparing the effectiveness of three intervention arms (acellular ECM, Oasis® and a cellular ECM, fibroblast-only Dermagraft®) and a standard treatment arm.

EFFICACY ENDPOINTS:

PRIMARY EFFICACY OUTCOME

1. Complete closure of ulcer by Week 12

SECONDARY EFFICACY OUTCOME

1. Complete closure of ulcer by Week 20
2. Rate of ulcer healing

3. Cost effectiveness comparing Oasis® and Dermagraft®

QUALITY OF LIFE ASSESSMENT: We will also evaluate the cost-effectiveness of the Oasis® compared to Dermagraft® and the standard of care by measuring QALYs as the measure of effectiveness, based on results obtained from SF-36v2™ questionnaire. Multiple regression will be used to allow to evaluate continuous dependent variable outcomes, including change scores between baseline and end of study physical (PCS) and mental (MCS) component summaries from the SF-36v2TM questionnaire.

DATA ANALYSIS: The primary outcome is wound closure by Week 12, will use Chi-square test to compare the percentages of subjects with complete closure in each group. Exploratory analysis with logistic regression, using the complete closure at 12 weeks as the dependent variable and the independent variables would include, treatment, size of ulcer, location on foot, how long ulcer has been present, previous revascularization, offloading compliance, concomitant medications, foot deformity, history of amputation, diabetes complications index, CRP level, and glucose control (HbA1c). Selection of covariates will be performed by stepwise modeling procedures.

Secondary outcomes, will use ANOVA or Kruskal-Wallis test to analyze cost effectiveness. depending if data is normally distributed for comparison of the three treatment arms. If significant, we will further analyze with pair-wise comparisons by using t-test or Wilcoxon rank-sum test with the Bonferroni correction to control for type I experiment-wise error rate of 0.05.

Rates of healing among the four groups will be analyzed using log-rank test to compare time of healing within 20 weeks.

Descriptive statistics will include demographics, smoking history, and characteristics of the wound. For comparison nominal categorical secondary outcome variables, we will use Chi-square test. For comparison of ordinal categorical variables, we will use the Wilcoxon rank-sum test (for two independent group comparison) and Kruskal-Wallis test (for three independent group comparison).

TABLE OF CONTENTS

- 1 BACKGROUND AND RATIONALE
- 2 OBJECTIVES
- 3 STUDY POPULATION
- 4 STUDY PROCEDURES
 - 4.1 DESIGN AND METHODOLOGY
 - 4.2 DESCRIPTION OF STUDY GROUPS
 - 4.3 STUDY FLOW CHART
 - 4.3.1 SCREENING/BASELINE PERIOD (VISIT 1 to 2/WEEKS -1 to -2)
 - 4.3.2 RANDOMIZATION (VISIT 3/WEEK 0)
 - 4.3.3 TREATMENT PHASE (VISIT 4/WEEK 1)
TREATMENT PHASE (VISIT 5/WEEK 2)
TREATMENT PHASE (VISIT 6/WEEK 3)
TREATMENT PHASE (VISIT 7/WEEK 4)
TREATMENT PHASE (VISIT 8/WEEK 5)
TREATMENT PHASE (VISIT 9/WEEK 6)
TREATMENT PHASE (VISIT 10/WEEK 7)
TREATMENT PHASE (VISIT 11/WEEK 8)
TREATMENT PHASE (VISIT 12/WEEK 9)
TREATMENT PHASE (VISIT 13/WEEK 10)
TREATMENT PHASE (VISIT 14/WEEK 11)
TREATMENT PHASE (VISIT 15/WEEK 12)
TREATMENT PHASE (VISIT 16/WEEK 13)
TREATMENT PHASE (VISIT 17/WEEK 14)
TREATMENT PHASE (VISIT 18/WEEK 15)
 - 4.3.4 STUDY ENDPOINT (VISIT 19/WEEK 16)
 - 4.3.5 FOLLOW-UP PHASE (VISIT 20/WEEK 17)
FOLLOW-UP PHASE (VISIT 21/WEEK 20)
FOLLOW-UP PHASE (VISIT 22/WEEK 24)
FOLLOW-UP PHASE (VISIT 23/WEEK 28)
- 5 ADVERSE EVENTS
- 6 STATISTICAL DESIGN
- 7 REFERENCES
- 8 APPENDIX

1 BACKGROUND AND RATIONALE

Diabetic foot ulcers (DFU), chronic, non-healing wounds, pose a serious problem to our healthcare system. Those with DFU are at higher risk for developing infections, which lead to limb amputations. The long-term effects are detrimental on quality of life and productivity loss. Within the VA system, diabetics with foot ulcers account for significant amount of sums of money to treat wounds and to improve healing in DFU. Thus far, studies have shown that the current standard of care to heal wounds is about 10-20% slower after 12 weeks of treatment compared to advanced therapy regimens. This unfavorable cure rate has prompted increased research for therapeutic alternatives, and novel approaches including topical application of growth factors, extracellular matrix scaffold materials and bioengineered living tissue replacements have been developed. This study plans to address the question of the comparative effectiveness of wound care modalities that could potentially translate into millions of dollars of savings for our health care system, as well as simplification of the treatment regimens for our patients—all without sacrificing clinical outcome. We propose to compare the clinical efficacy of two of the most expensive novel treatments for DFU, bioengineered cell-based bioengineered extracellular matrix tissues containing living dermal fibroblasts (Dermagraft®) to a device that is 15-fold less expensive but has related biologic rationale—an extracellular matrix scaffold devoid of living cellular elements (Oasis®). We hypothesize that these three treatments will yield equivalent clinical outcomes, supporting the adoption of the less expensive, cell-free, matrix device. The importance of this study would then be to establish a protocol approach to wound care that would be implemented system wide.

2 OBJECTIVES

The primary objective of this study is to assess the effectiveness of cellular dermal replacement tissue vs. non-viable extracellular matrix (ECM) for the treatment of non-healing diabetic foot ulcers. The primary endpoint will be the measurement of wound closure at 12 weeks, secondary outcomes will be measured at 20 weeks and the rate of healing in each treatment arm.

The secondary objective of study is to determine cost effectiveness of the bioengineered cellular vs. acellular ECM products. Cellular ECMs (Dermagraft®) are costly devices, \$1800 per application, difficult to use and time sensitive (weeks). The acellular ECM (Oasis®) is easier to use and at a cost \$80 per application and has a longer shelf life (2 years). These devices typically require multiple applications, on a weekly basis. If the findings show that these devices are equivalent, then the use of acellular ECM would lead to significant savings for the VA. Genetic markers of non-healing vs. healing diabetic ulcers will also be investigated, which will be useful information in predicting healing potential.

[figure not shown]

Each subject will be given a unique identifier that will have no personal information linked after assignment of a randomly computer generated list of three repeated numbers which will be available for each site. The request for assignment will be emailed to the Data Coordinator with a completed eligibility form, and no personal identifiers except for initials and a last 4 digits of social security. The Data Manager will assign a number and the next sequential group assignment with each subsequent request will be placed in sealed envelopes. Subject demographics will not be provided until this assignment is complete. Participants will be randomly placed into the standard therapy, Oasis® or Dermagraft® groups. There will be an estimated of 57 patients in each group.

The patients will not be informed of treatment administered. However, due to the handling of the Dermagraft® (packaging and thawing), whereas Oasis® is readily available at room

temperature, the Investigator/clinician will be able to identify the two treatments. Therefore, to avoid assessment bias, we will have an Inter-observer that will be blinded to treatment to perform all follow-up wound evaluations and record measurements. Following measurement/wound assessment, the treatment will be performed by another assigned clinician, which will not the involvement of the Inter-observer.

Withdrawal:

The subjects may withdraw from the study at any time during the study, upon request. The investigator may also discontinue a subject if it is determined that the subject has not responded to therapy or adverse event occurred, which requires alternative therapy. Those subjects that have undergone treatment will be followed and documented until end of the study. If there is more than 10 percent loss to follow-up, then investigators will attempt to recruit additional subjects.

4 STUDY PROCEDURES

4.1 DESIGN AND METHODOLOGY

We propose a randomized, single blinded, three-armed controlled clinical equivalence trial comparing the effectiveness of two intervention arms (acellular ECM, Oasis® and cellular ECM, Dermagraft®) and a standard treatment arm to address the problem of efficacy and cost effectiveness among synthetic skin grafts in treating DFUs in the VA system

4.2 DESCRIPTION OF STUDY GROUPS

Standard (Conventional) Therapy:

Standard therapy will consist of the typical foot evaluation and care provided by the Department of Veteran Affairs facilities, which will include weekly sharp debridement, cleansing of wound with normal saline, and application of non-adhesive dressing (Adaptic® or Mepitel®), Iodosorb® gel over wound bed, covered by dry dressings. The investigator will document the standard care provided during clinic visits including weekly follow-up evaluations. Offloading will be standardized, which will involve placement in modified offloading insert (trilaminar plastazote) and removable Cam Walker boot.

Oasis®:

Patients in the Oasis® group will undergo the same wound care and offloading modality as the Standard Therapy group, with weekly wound evaluation dressing changes. The Oasis® matrix will be applied on the wound (cut to size), moistened with normal saline to assure adherence to wound bed, then apply non-adhesive dressing (Adaptic® or Mepitel®), moist sterile gauze, dry and gauze dressings. Up to 8 weekly applications will be applied to wound until healed.

Dermagraft®:

Patients in the Dermagraft® group will receive the same Standard Therapy, with weekly wound evaluation and dressing changes. The Dermagraft® will be thawed as directed by the manufacturer, then under sterile technique Dermagraft® will be cut to size of wound, covered with non-adhesive coverage (Adaptic® or Mepitel®), moistened sterile gauze and dry dressings. Up to 8 weekly applications will be applied to wound until healed.

4.3 STUDY FLOW CHART

Study Plan Schematic

Procedure	Visit 1 (Week -2)	Visit 2 (Week -1)	Visit 3 (Week 0) Randomization	Visits 4-10 (Week 1-7) Treatment	Visits 11-18 (Week 8-15) Treatment	Visit 19 (Week 16) Study Endpoint	Visits 20-23 (Week 17-28) Follow-Up
Informed Consent	X						
Inclusion/Exclusion Criteria	X	X	X				
Physical Exam	X					X	
Vital Signs	X	X	X	X	X	X	
Ankle-Brachial Index	X						
Fungal Infection Culture and Malignancy Evaluation	X						
Blood Sample Drawn for Labs	X						
SF-36v2™, EQ-5D, QALYs Questionnaires	X						Visit 20 only
Ulcer Assessment	X	X	X	X	X	X	X
Debridement	X	X	X	X	X	X	X
Ulcer Photography and Area Measurement	X	X	X	X	X	X	X
Randomization			X				
Dermagraft® Tx + SOC			X	X			
Oasis® Tx + SOC			X	X			
SOC	X	X	X	X	X	X	X
Concomitant Medications	X	X	X	X	X	X	X
Adverse Events	X	X	X	X	X	X	X

4.3.1 Screening/Baseline Period (Visit 1, 2/Week -2, -1)

Subjects that meet all criteria of the study will be given an informed consent form to review and sign. Subjects will be required to complete all screening assessments within the 2 weeks prior to randomization and start of treatments.

Screening assessments and pre-treatment:

- 1) Demographic information: gender, age, race, socio-economic status.
- 2) Medical history: medical problems, surgeries, trauma, history of previous ulcers, amputations, characteristic and duration.
- 3) Physical examination: vital signs, height, weight, Body Mass index
- 4) General health and lifestyle: smoking history, alcohol, drugs abuse, regular physical activity.
- 5) Lower extremity exam: vascular - pedal pulses, color of skin, temperature, edema; dermatological – clinical description of the ulcer (staging per UT wound classification), fungal infection of skin and/or nails, skin integrity (calluses, dryness); musculoskeletal – foot deformities such as bunion, hammertoe, bony prominence, fat pad atrophy, altered gait; neurological – absence or presence of sensation with 5.07/10 Semmes-Weinstein monofilament, reflexes.
- 6) Non-invasive vascular study: ankle-brachial systolic pressure (ABI) and toe-brachial systolic pressure (TBI). In order to meet criteria, ankle-arm index must be equal to or greater than 0.8 and less than 1.4 or a toe-arm index is equal to or greater than 0.6.
- 7) Foot ulcer history (location, length of time, treatments used, pain, etiology of ulcer).
- 8) Laboratory: HgA1c, chemistry, CBC, pregnancy test (for women of childbearing ages), LFT, ESR, CRP and albumin.

- 9) Radiological imaging – plain foot and/or ankle films for baseline.
- 10) Subjects will be given the health-related quality of life survey, the Medical Outcomes Study 36 item Short Form (SF-36v2™) health survey.
- 11) Sharp debridement of ulcer will be performed per standard method. A small sample will be collected for microbiology (gram stain, cultures/sensitivities, and fungal) and pathology.
- 12) Photographs of ulcer will be obtained before and after debridement, using Silhouette Mobile™ ulcer tracing, surface area calculation.
- 13) Dressings applied will include non-adhesive dressing (Adaptic® or Mepitel®), Iodosorb® gel over wound bed, covered by dry dressings.
- 14) Off-loading shoes will be given, modified offloading insert (trilaminar plastazote) as determined appropriate per discretion of clinician.

4.3.2 Randomization (Visit 3/Week 0)

Those subjects that meet all eligibility criteria will be randomly assigned to one of the three groups. A randomized number will be assigned to each subject participating in the study, where one will receive either Dermagraft®, Oasis® or the control (standard therapy).

4.3.3 Treatment Phase (Visits 4 to 18/Weeks 1 to 15)

Subjects will be evaluated and receive treatments on weekly basis (7 days +/- 2 days).

Appointments will be made as determined by investigator at each VA facility.

- At each visit, vital signs will be obtained and recorded.
- The ulcer will be assessed – visual inspection – complete ulcer characteristics form (see appendix).
- If there is concern for infection after evaluation of ulcer, then a confirmatory bacterial culture will be obtained (deep swab culturette or tissue specimen/biopsy). Radiographical xrays and blood work (CBC, ESR, CRP, and Chem) may also be performed if deemed necessary by investigator clinician.
- Next, a digital image will be taken one image before debridement and one image immediately after debridement (camera will capture dimensional size of ulcer). The images will be stored on a central server, with unique identifier as well as loaded on CPRS Vista imaging.
- Surgical debridement of ulcer will be performed using curette or blade. Clinician should debride wound to promote mild bleeding from ulcer site and removal of necrotic or fibrinous tissue and excess hyperkeratotic margins if possible. Clinician may use lidocaine topical jelly/ointment if ulcer is too tender to debride.
- All wound beds will be cleaned gently with normal saline 0.9%.
- Application of treatments:
 - Standard (Conventional) Therapy:
Application of non-adhesive dressing (Adaptic® or Mepitel®), Iodosorb® gel over wound bed, covered by dry gauze dressings.

Oasis®:

The Oasis® matrix will be applied on the wound (cut to size using scissors), moistened with normal saline to assure adherence to wound bed, then apply non-adhesive dressing (Adaptic® or Mepitel®), moist sterile gauze, dry and gauze dressings. Up to 8 weekly applications will be applied to wound until healed.

Dermagraft®:

The Dermagraft® will be thawed as directed by the manufacturer, then under sterile technique Dermagraft® will be cut to size of wound using scissors,

covered with non-adhesive coverage (Adaptic® or Mepitel®), moistened sterile gauze and dry dressings. Up to 8 weekly applications will be applied to wound until healed.

- Offloading devices:
 - Plantar foot ulcers – offload with post operative style shoe (with plastazote cut out (perature or extravasation) as necessary to offload ulcer pressure area.
 - Heel ulcers – use multi-podus splint or Rooke boot.
- Changes in concomitant medications, adverse events, compliance to offloading, will be recorded.
- If ulcers heal sooner than 8 weeks, the subject will be assessed the following week. Ulcer healing is defined by 100% epithelization as determined by the clinician. The subject with healed ulcer will also return for follow-up visits Weeks 9, 16, 20.

NOTE: if ulceration remains open after 8th application – then will switch back to standard of care therapy (if budget allows, may consider extending graft course).

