4.3.4 Study Endpoint (Visit 19/Week 16)

- Subjects to complete the health-related quality of life survey, the Medical Outcomes Study 36 item Short Form (SF-36v2™) health survey.
- Vital signs will be obtained and recorded.
- The ulcer will be assessed – visual inspection – complete ulcer characteristics form (see appendix). Determine if reaches 100% epithelization determined by clinician.
- Labs drawn from each subject, hematological and chemistry panel. Pregnancy test of childbearing age.
- If concern for infection, confirmatory bacterial culture will be obtained (deep swab culturette or tissue specimen/biopsy). Radiographical x-rays and blood work (CBC, ESR, CRP, and Chem) may also be performed if deemed necessary by investigator clinician.
- Digital imaging of ulcer location, if remains non-healing then 2 images to be obtained prior to and after surgical debridement.
- Surgical debridement of ulcer if not healed, will be performed using curette or blade and standard therapy.
- Changes in concomitant medications, adverse events, compliance to offloading, will be recorded.

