6 STATISTICAL DESIGN

Measures:

Measures will be collected at baseline, weekly thereafter, with primary endpoint of complete healing at Week 12, and final secondary endpoint measurement at Week 20. The ulcer will be assessed weekly and will be treated as described above. A designated inter-observer will be at each of the testing sites, (blinded to the treatment of the subjects) which will perform all measurements. The following measurements will be taken: size (surface area calculation), photos (digital includes ruler) and complete foot ulcer assessment (description of ulcer/characteristics), before and after debridement. Subjects where ulceration healed earlier than Week 12 will have follow-up assessment one week after healing, then at Week 12 and 20. If ulcerations healed after 12 weeks, then the subjects will be assessed at one week after healing and at Week 20. There will be 4 follow-up visits (Weeks 17, 20, 24, 28), assessed every 4 weeks for a total of 16 weeks.

During the study, if ulceration appears to be infected as determined by clinical presentation characterized by the presence of two or more signs of inflammation,³ the clinician will follow the protocol of obtaining wound culture for microbiology, radiographs, blood work (CBC, chemistry panel, sedimentation rate, and C-reactive protein), and treatment immediately with appropriate antibiotics. Subjects with infected ulcers will be withdrawn from study and investigators will be notified. In addition, adverse events will be well documented and treated per protocol, and subjects will be withdrawn from study.

Clinical Outcomes:

- The percentage of subjects that have complete closure of ulceration by Week 12 and Week 20. Complete healing will be defined as full re-epithelialization with no drainage, or callus formation and remains closed after 1 week of wound closure.
- Rate of wound healing to achieve complete closure. Weekly measurements of surface area will be recorded on a grid marked acetate sheet, using a metric ruler to determine length and width of the wound.
- A diabetic foot ulcer assessment form will be filled out at weekly follow-up visits, that describes characteristics of ulceration including peri-ulcer erythema, wound margins, fibrin, granular tissue, peri-ulcer pruritus, edema and location, pain, amount of drainage and type, amount of epithelialization, pain level, depth, and bioburden.

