- Number of incident subjects with infection, osteomyelitis and acute Charcot during the study, will be withdrawn from the study.
- Number of incidence of adverse effects will be reported from all sites, and will be withdrawn from the study.
- Veterans' Short Form Health Survey (SF-36v2TM), a self-administered questionnaire will be used to measure quality of life, given at beginning and at the end of the study.
- EuroQol Questionnaire (EQ-5D) to evaluate overall quality of life and to facilitate the calculation of health utilities and quality adjusted life years (QALYs). The EuroQol questionnaire (EQ-5D) will be administered at beginning and at the end of the study.

Sample Size Estimation:

The sample size was estimated based on 80 percent power, significance level 0.05, to detect a difference in the incidence of ulcer closure of the two study groups and the standard of care group (Stplan4.3).⁴ It is expected that 50% of the Dermagraft® and Oasis® groups will reach complete ulcer closure by Week 12 and approximately 25% closure with those subjects that received the standard of care (numbers based on previous studies as described previously). We would expect the difference to be 25% between the standard and the treatment group. By using a Chi-square test without continuity correction test would require 57 subjects in each group. If we estimate the difference to be 20% and lower of the cure rates to be 30%, then we would require 88 patients in each group.

Analyses:

The primary end point is wound closure by Week 12, which will be analyzed using Chi-square test to compare the percentages of subjects with complete closure in each group. We will also perform exploratory analysis with logistic regression, using the complete closure at 12 weeks as the dependent variable and the independent variables would include, treatment, size of ulcer, location on foot, how long ulcer has been present, previous revascularization (will analyze as subset group), offloading compliance, concomitant medications, foot deformity, history of amputation, diabetes complications index, and glucose control (HbA1c). Selection of covariates will be performed by stepwise modeling procedures.

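### Suspected infection is handled by two conflicting rules with no named assessor, so infection and osteomyelitis counts and withdrawals before Week 12 are open to ascertainment bias

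*Combined protocol and SAP*

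**What the plan says.** Three sections of the protocol deal with an ulcer that may be infected.

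- **Section 6, Measures.** The rule applies throughout the study "if ulceration appears to be infected as determined by clinical presentation characterized by the presence of two or more signs of inflammation". In that case "the clinician will follow the protocol of obtaining wound culture for microbiology, radiographs, blood work", with the blood tests listed. Antibiotics follow at once, and the subject is withdrawn.
- **Section 4.3.3 (Weeks 1 to 15).** "If there is concern for infection after evaluation of ulcer, then a confirmatory bacterial culture will be obtained". X-rays and blood tests are optional: "Radiographical xrays and blood work (CBC, ESR, CRP, and Chem) may also be performed if deemed necessary by investigator clinician".
- **Section 4.3.4 (Week 16).** The wording is nearly the same: a culture on concern, while x-rays and bloods "may also be performed if deemed necessary by investigator clinician". Separately, every subject has a haematology and chemistry panel at this visit.

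On blinding, Section 3 says that "the Investigator/clinician will be able to identify the two treatments". It therefore gives all follow-up wound evaluations to an observer who does not know the treatment. Section 6 gives the same observer all measurements, including the full ulcer assessment before and after debridement.

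Among the clinical outcomes, Section 6 lists "Number of incident subjects with infection, osteomyelitis and acute Charcot during the study" and says that these subjects are withdrawn.

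**The concern.** At a treatment visit where an ulcer shows two inflammatory signs, Section 6 requires radiographs and bloods while Section 4.3.3 makes them optional. Two sites could each follow the protocol and investigate differently. So could one clinician with two patients in different arms.

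Two things are at stake. The first is the set of counted outcomes: infection depends on which trigger is used and who applies it, and osteomyelitis depends on how far the subject is investigated. The second is the primary endpoint: an infection call removes the subject from the study, possibly before Week 12. The clinician's knowledge of the product is already recognised in Section 3 as a source of assessment bias, but the safeguard set up there is not explicitly extended to the infection call.

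**Working it through.** **Step 1. The rules side by side.**

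| Element | Section 6 | Sections 4.3.3 and 4.3.4 |
|---|---|---|
| Trigger | At least two inflammatory signs | Concern, not defined |
| Culture | Required | Required, described as confirmatory |
| X-rays | Required | Optional |
| Blood tests | Required | Optional (at Week 16 haematology and chemistry are drawn from everyone, which leaves ESR and CRP) |
| Who decides on x-rays and bloods | No discretion | Investigator clinician |
| Who makes the infection call | Not named | Not named |

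The trigger differs, and x-rays and bloods have a different status. Culture does not differ. Section 4.3.5 (Weeks 17 to 28) has no infection step, although Section 6 speaks of the whole study. Section 6 acts on clinical presentation, whereas 4.3.3 and 4.3.4 call the culture confirmatory; the effect of a negative culture on the call is not stated.

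**Step 2. Which outcome could move, and how.**

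- *Infection.* Section 6 identifies it by signs, so optional x-rays and bloods need not change this count. The exposure comes from the two triggers and the unnamed assessor.
- *Osteomyelitis.* No case definition is given for incident cases. Bone biopsy, MRI or bone scan appear only in exclusion criterion 7. Uneven investigation could produce uneven counts, but plain x-ray is not among those methods, so the link is indirect.
- *Withdrawal.* Each subject is 1/57 = 1.75 percentage points of closure in an arm of 57. Section 3 says that treated subjects who leave are followed to the end of the study. The analysis text in Section 6 and in the SAP does not say how withdrawn subjects are counted at Week 12.

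**Step 3. Size.** The plan states no infection, osteomyelitis or detection rate, so there is no figure to reproduce and no basis for an estimate. The following only shows how the mechanism scales. Assume the same true risk r in two arms of 57 (Section 6) and a proportion d of cases recorded.

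Expected recorded cases = 57 × r × d. Apparent risk ratio = d(first arm) / d(second arm).

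| r (assumed) | d = 90% | d = 70% | d = 50% |
|---|---|---|---|
| 10% | 5.13 | 3.99 | 2.85 |
| 20% | 10.26 | 7.98 | 5.70 |
| 30% | 15.39 | 11.97 | 8.55 |

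The apparent risk ratio is 0.90/0.70 = 1.29 or 0.90/0.50 = 1.80 at every r, and 1.00 if recording is equal. Nothing in the documents says which of these applies, or in which direction.

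**The case against.** The case for treating this as a small wording matter is substantial, and much of it stands.

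- *A reader might infer that the whole work-up is discretionary.* It is not. Culture is required in all three sections, and at Week 16 part of the blood work is drawn from everyone. This objection stands.
- *A reader might infer that an unblinded clinician makes the infection call.* The documents do not say so. Discretion is given to the investigator clinician only for x-rays and bloods. In 4.3.3 concern arises from the ulcer evaluation, and Section 3 gives follow-up evaluations to the blinded observer. The assessor is unnamed, not stated to be unblinded. This stands, but it leaves a gap that needs filling.
- *The sections may describe tiers:* concern leads to culture, two signs to the full work-up. That would be coherent, but no section says it, and an ulcer with two signs falls under both rules.
- *The comparison is not a principal one.* Infection is not among the efficacy endpoints, and the analysis text names no infection comparison. True, but it is a listed clinical outcome and a cause of withdrawal.
- *Random error would be about as large as the bias.* At r = 20% with 90% and 70% recorded, the rates are 18% and 14%, a gap of 4 points. The standard error is √[(0.18×0.82 + 0.14×0.86)/57] = 6.9 points. With 90% and 50% recorded, the gap is 8 points and the standard error 6.5. This defeats any claim that the comparison becomes uninterpretable. It does not remove a bias that wording could prevent.

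**Conclusion.** The point holds in a limited form. Sections 4.3.3 and 4.3.4 conflict with Section 6 on the trigger and on whether x-rays and bloods are required. The person who makes the infection call is not named, and the discretion that does exist lies with a clinician who can recognise the product. Infection and osteomyelitis counts, and withdrawals before Week 12, are therefore open to ascertainment bias. For osteomyelitis the route is mainly optional investigation; for infection it is the trigger and the assessor.

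The size is unknown. The ratios of 1.29 and 1.80 rest wholly on assumed recording rates and show possibility, not a forecast. The documents do not support the stronger inferences that bone infection will be missed in one arm or that the safety comparison is lost. This is a modest defect, worth correcting because the correction is cheap.

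**What to change.** 1. Reconcile Sections 4.3.3, 4.3.4 and 6 so that one trigger and one work-up rule apply at every visit in every arm. Which clinical rule to keep is for the investigators.
2. For the outcome count, state that infection is classified from the blinded observer's weekly ulcer assessment. The Ulcer Characteristic Form already records peri-wound erythema and edema, drainage and pain. Section 6 cites an outside source rather than listing the signs, so the sponsor must specify which form items count.
3. At each triggered visit, record whether the work-up was done, so that differences in investigation between arms can be seen.
4. Report infection and osteomyelitis by arm in all randomised subjects.

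Item 2 governs classification for analysis only; care decisions stay with the clinician. The cost is protocol wording, one form field and possibly a few more tests, depending on the rule kept. No added staff role is needed, since the blinded observer is already in the plan.
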